3.1.3 Allocation ratio

The Tech intervention contrasted two function sets—Lite-Tech (40% allocation), which was a minimalistic toolset focused on providing basic data to the patient, and Full-Tech (60% allocation), a more expansive toolset. The Touch intervention contrasted two training approaches—Low-Touch, a self-guided approach where patients could view built-in tutorials, and High-Touch (initially 50% allocation), where patients receive in-person guided training with the technology. The realized allocation ratios are presented in Table 2.

Table 2. Realized allocation ratio.

Tech Allocation	Touch Allocation		Total
	High	Low	
Full			
Frequency	624	1,523	2,147
Row %	29.1%	70.9%	100.0%
Column %	69.3%	76.5%	74.2%
Overall %	21.6%	52.7%	74.2%
Lite			
Frequency	277	468	745
Row %	37.2%	62.8%	100.0%
Column %	30.7%	23.5%	25.8%
Overall %	9.6%	16.2%	25.8%
Total			
Frequency	901	1,991	2,892
Row %	31.2%	68.8%	100.0%
Column %	100.0%	100.0%	100.0%
Overall %	31.1%	68.8%	100.0%

The assignment protocol used three phases where the Touch allocation ratio was changed by the research team.

1. In Phase 1, patients received the High-Touch intervention only after consenting to the study and submitting their Admission survey (see Section 3.8.2). Low-Touch patients could view the tutorial at any point and were not required to complete the Admission survey. Phase 1 assigned patients to High/Low-Touch in a 1:1 ratio.
2. In Phase 2, beginning in February 2018, the study shifted to a 3:1 ratio of High/Low-Touch. This change was done to ensure that sufficient individuals were assigned to the High-Touch intervention due to under-enrollment. Quality monitoring of the study found a number of exogenous factors that were impacting the High-Touch intervention, including, but not limited to: patient discharges; patient moved to other rooms; patient not present during TN rounding; patient was engaged with the care team and unable to work with the TN; and tablet returned prior to receiving an intervention. This change in the ratio was intended to increase the number of patients who would be eligible to receive a High-Touch intervention while maintaining the *per protocol* approach in that these exceptions were considered a component of the Protocol.

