#### 1.4.2 Analytic framework

A review of factorial randomized control trials identified that the appropriate analytics model, in general, would adhere to Equation 1 (see below), assuming that the basic functional form for regression is the appropriate approach. This approach was used per Montgomery et al. Variations to this functional form are noted below.

$$\text{Eq. 1: } y = X_{Tech} + X_{Touch} + X_{Tech*Touch}$$

To address potential differences in variance associated with the multi-site and pragmatic aspects of the study (e.g., expansion of the study after it was originally conceptualized and operationalized, differences in policies and procedures across hospitals and units), we performed cluster-robust standard errors in the estimation of the outcomes. The analysis clusters study participants by the hospital where the study participant was enrolled. To validate this assumption, a sensitivity analysis was performed on patients transferred to different hospitals within the medical center.

Further, to account for heterogeneity in duration of patient access to the inpatient portal, we included the length of tablet provisioning, measured in days, as an offset parameter in all models.

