#### **1.4.4 Distributional assumptions**

Prior to analysis, we will conduct an examination of the data to assess model fit for each hypothesis (i.e., Poisson, Negative Binomial, etc.).i

---

i Preliminary analysis revealed wide variance in the length of time that patients had a tablet, which we termed ‘provision length’. This provision length was included as an exposure in the model fitting process. Analysis after data collection suggested that the ANOVA model was a poor choice for the distribution of the data. Poisson models were excluded because of the foundational assumption—namely that the mean and variance of the response variable are the same. In the data, the variance was significantly greater than the mean, leading this model to significantly underestimate true variability in the data. Subsequent outlier analysis suggested no improvement. The negative binomial model was specified four ways: (1) negative binomial; (2) negative binomial with the provision length adjustment; (3) zero truncated; (4) zero truncated with the provision length adjustment. The zero truncated model with length of provision as an exposure variable provided the best relative fit when comparing information criteria values. However, this improvement was viewed as marginal relative to the negative binomial model specification. For this reason and to account for the heterogeneity in provision length, all count outcomes were fit using a negative binomial model with the provision length adjustment.

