### 1.5 Hypothesis 1: Inpatient portal use

*H1: Individuals assigned to the High intervention levels for Tech and Touch will demonstrate higher use of MyChart Bedside.*

We operationalized higher use in this hypothesis in three ways:

1. Frequency of use
2. Comprehensive use

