#### 1.5.1 Outcome 1 – Number of MyChart Bedside sessions within the enrollment admission was dependent on treatment

*Dependent variable specification:* The count of MyChart Bedside sessions for the admission associated with study enrollment.

- Enrollment admission was defined as the admission when the patient was enrolled in the study.

*Statistical model:* Negative binomial model with non-interacted and interacted study arms as binomial predictors.

---

ii Preliminary analysis of adoption rates for the outpatient portal revealed a rapid decrease in the numbers following the first few months, which motivated us to set the value for the cutoff date at 90 days in order to more conservatively attribute portal use to an individual's participation in the study.

*Covariates:* No covariates were added to this analysis.

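### H1 Outcome 1 is defined as a session count, but the only effect reported is sessions per day of tablet possession, a period that ends after assignment; a total-use estimate is needed beside it

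*SAP*

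**What the plan says.** SAP 1.5 states the hypothesis as "Individuals assigned to the High intervention levels for Tech and Touch will demonstrate higher use of MyChart Bedside". SAP 1.5.1 defines the first outcome as "The count of MyChart Bedside sessions for the admission associated with study enrollment", analyzed by negative binomial regression on the study arms, and adds "No covariates were added to this analysis".

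The exposure adjustment is set elsewhere. SAP 1.4.2 says that, "to account for heterogeneity in duration of patient access to the inpatient portal, we included the length of tablet provisioning"; it enters every model as an offset, in days. The footnote to SAP 1.4.4 reports "Preliminary analysis revealed wide variance in the length of time that patients had a tablet", compares four negative binomial specifications by information criteria, and concludes that "all count outcomes were fit using a negative binomial model with the provision length adjustment".

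On the timing of possession:
- Tech is determined by medical record number digits that exist before study assignment (Protocol 3.2.1). Touch is assigned at consent (3.2.2) or shortly before it (3.3).
- Only patients already provisioned with the portal are recruited (5.1.1, 5.2).
- Protocol 3.1.3 lists "tablet returned prior to receiving an intervention", separately from discharge, among the obstacles to High-Touch delivery.

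Neither document says when provision length starts or stops, reports it by arm, or considers whether assignment could change it. The model without provision length was fitted only to compare model fit. No effect estimate from it is planned.

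**The concern.** An offset in a log-link model fixes the coefficient of log days held at one, which turns a count into a rate. The outcome that SAP 1.5.1 defines and the quantity that SAP 1.4 estimates are therefore different.

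The difference matters if the denominator can respond to the intervention. Ten selectable functions instead of three, or guided training, could give a patient a reason to keep the tablet, or could lead a patient to finish with it sooner. Extra sessions gained by keeping the tablet longer are part of higher use as H1 words it, yet the offset removes them. If use is heaviest soon after hand-out, longer possession also lowers the daily average. H1 is a primary hypothesis, and without a second model a reader cannot tell an effect on intensity from an effect on total use.

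**Working it through.** **Plan's own figures.** The only sample-size statement (Protocol 3.4: 3,872 patients, detectable changes of 2.2% to 3.8%) concerns satisfaction scores. The plan gives no figure for session counts or days held, so there is nothing to reproduce on this point.

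**Step 1: what the offset estimates.** Let Y be sessions, D days held and x the arm. The 1.4.4 footnote calls provision length an exposure, so I take it to enter as log D:

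log E(Y) = log D + b0 + b1·x

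Then exp(b1) is a ratio of sessions per tablet-day, approximately:

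offset ratio = count ratio / duration ratio

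**Step 2: range of distortion.** The duration ratio is not in the documents. I assume 0.9 to 1.3.

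| Count ratio | 0.90 | 1.00 | 1.05 | 1.10 | 1.20 | 1.30 |
|---|---|---|---|---|---|---|
| 1.10 | 1.22 | 1.10 | 1.05 | 1.00 | 0.92 | 0.85 |
| 1.20 | 1.33 | 1.20 | 1.14 | 1.09 | 1.00 | 0.92 |

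Columns are duration ratios and cells are offset ratios. A cell falls below 1 only where the duration ratio exceeds the count ratio.

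**Step 3: fitted models.** These are simulated negative binomial fits with 901 against 1,991 patients (the Touch totals in Protocol Table 2, illustrative only), 200 replicates per scenario and an assumed median of 4 days held. Sessions grow as D to the power g.

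| Duration ratio | g | Direct ratio | No offset | With offset |
|---|---|---|---|---|
| 1.0 | 1 | 1.2 | 1.19 | 1.19 |
| 1.0 | 0.5 | 1.2 | 1.20 | 1.21 |
| 1.2 | 1 | 1.0 | 1.21 | 1.00 |
| 1.2 | 0.5 | 1.0 | 1.10 | 0.92 |
| 1.2 | 0.5 | 1.2 | 1.31 | 1.10 |
| 0.9 | 0.5 | 1.0 | 0.95 | 1.06 |

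When possession does not depend on arm, the two models agree, the null rejection rate with the offset is 3% to 3.5%, and power can rise (79% to 99.5% in the first row). When an arm lengthens possession, its effect shrinks. It reverses in the fourth row, where the offset estimate was below 1 in about 95% of replicates. When an arm shortens possession, a 5% fall in sessions appears as a 6% rise.

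**Step 4: how much early return a reversal needs.** Assume stay = 3 + an exponential with mean 4 days, and return time = 0.25 + an exponential with mean 4k. Days held is the smaller of the two. Use starts at 2 sessions per day and decays at 0, 0.15 or 0.30 per day. The control arm has k = 1 and the better arm k = 1.5, so the duration ratio is about 1.22.

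- No direct effect: total ratios 1.22, 1.16, 1.13; offset ratios 1.00, 0.96, 0.93.
- Direct rate ratio 1.10: offset ratios 1.10, 1.05, 1.02, so no reversal.
- Share returned before discharge = 1 − exp(−2.75/4k)·k/(1+k). For k = 1 this is 1 − 0.503 × 0.5 = 75%. For k = 1.5 it is 1 − 0.632 × 0.6 = 62%.
- With about 34% early return in the control arm, the same 1.5-fold change gives a duration ratio of 1.08. With about 12% it gives 1.03, and the offset ratio is then 0.98 to 1.00.

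**Step 5: an exposure that runs to discharge.** In the k = 1.5, no-direct-effect case, using length of stay as the exposure (tablet assumed issued at admission) gives 1.19, 1.15, 1.12. The direction is right throughout and the values lie close to the total-session ratios.

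**The case against.** The best defence is that sessions per day of access is a legitimate measure of use, chosen for a stated reason and supported by model comparison. If possession does not depend on arm, it preserves the null and gains precision. That stands, and it is why the rate model should be kept. Better information criteria do not, however, show that an exposure is unaffected by treatment.

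The second defence is that nothing in the documents shows an arm difference in possession. The returns named in Protocol 3.1.3 came before training, so training cannot have caused them, and the protocol calls these factors exogenous. Hand-out was blind to Tech (Protocol 3.3) and normally preceded Touch assignment, so part of the period lies outside the reach of Touch. All of this stands. It protects the start of the period better than its end: no blinding to the portal version during use is described, and return comes after assignment to both factors.

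A reader might go further and infer that the plan does remove part of the effect, or gives it the wrong sign. The documents do not support that. They give no days held by arm, and the distortion could run either way. In Step 4, reversal required no direct effect on daily use and early return by about 75% of control patients. No section reports such a proportion.

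Nor is the offset in conflict with the statement that no covariates were added. An exposure with a fixed coefficient is not a covariate in the usual sense.

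**Conclusion.** The point holds as a mismatch between outcome and estimate. H1 Outcome 1 is a count for the admission, the sole planned effect is a rate per tablet-day, and the denominator closes after assignment. Whether this distorts the answer on total use depends on whether Tech or Touch changes days held, which the documents leave open.

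The size is therefore conditional. The estimate is multiplied by about 1 / (duration ratio): nothing at 1.0, 0.83 at 1.2 and 1.11 at 0.9. A change of sign needs possession to rise proportionally more than sessions. These figures assume that provision length enters on the log scale and that the duration ratios are as chosen above. The case is stronger for Tech than for Touch. The change should be made because it is cheap and concerns a primary hypothesis, not because bias has been shown.

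**What to change.** For H1 Outcome 1:

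1. Report a negative binomial model of the session count whose exposure does not depend on tablet return. Use log time from first provisioning to discharge of the enrollment admission, with discharge taken from the merged admission/discharge/transfer records (Protocol 6.3.2), or use no offset. Base the conclusion on total use on this model.
2. Report the provision-length model beside it, labelled as intensity of use while the tablet was held.
3. Define the start and end of provision length, and report days held by arm.

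The cost is one more model and one table. Discharge times are in hand. Hand-out times should be recoverable from whatever produced provision length, although Protocol 6.2 does not list them; if they are not, the version without an offset needs none. Tablets withdrawn for logistical reasons will add some noise, and precision may be lower than with the rate model. Time to discharge is itself settled after assignment, so the first form assumes that the interventions do not change it. The version without an offset does not need that assumption.

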#### 1.4.8 Cutoff date determination

Two options were considered for both the pre-study enrollment and post-discharge cutoff dates as specified in subsequent sections: 90 days (approximately three months) and 180 days (approximately six months) before/after the hospital encounter in which an individual was enrolled in the study. The actual cutoff date was determined after examining the cumulative distribution of MyChart adoption over the course of the year preceding/following hospital discharge to identify a meaningful endpoint.ii

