### **1.7.4 Outcome 4 – Frequency of use for New MyChart Users.**

*Outcome specification:* The count of MyChart sessions occurring between the date of enrollment in the study and the cutoff date. This variable was specified as a count variable. Prior MyChart Users and Never MyChart Users were not included in the analysis for this outcome.

*Statistical model:* Negative binomial regression model for counts of sessions with non-interacted and interacted study arms as binomial predictors (see Equation 3).

Equation 3: If New MyChart User=1;  $y = X_{Tech} + X_{Touch} + X_{Tech*Touch}$

*Covariates:* No covariates were added to this analysis.

*Sub-sample analysis:* No sub-sample analyses were considered for this outcome.

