### 1.7.5 Outcome 5 – Frequency of use for Prior MyChart Users

*Outcome specification:* The count of MyChart sessions occurring between the date of enrollment in the study and the cutoff date. This variable was specified as a count variable. New MyChart Users and Never MyChart Users were not included in the analysis for this outcome.

*Statistical model:* Negative binomial regression model for counts of sessions with non-interacted and interacted study arms as binomial predictors (see Equation 4).

Equation 4: If Prior MyChart User =1;  $y = X_{Tech} + X_{Touch} + X_{Tech*Touch}$

*Covariates:* The count of pre-enrollment sessions was included as a covariate in the model to control for previous use.

*Sub-sample analysis:* No sub-sample analyses were considered for this outcome.

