### 1.8.1 Outcome 1 – Self-efficacy

*Outcome specification:* The self-efficacy scale was scored as the mean of six individual 5-point Likert scale survey items and was promulgated in each of the surveys (i.e. Admission, 15-day Post-discharge, 6-month Post-discharge). The six items were:

1. I am confident I can change my behaviors to improve my health.
2. I am confident that I can work with my provider to improve my health.
3. I am confident that if prescribed a new medication, I can take it appropriately.
4. I am confident that I can do the different tasks and activities needed to manage my health condition(s).
5. I am confident that I can keep symptoms or health problems from interfering with the things I want to do.
6. I am confident that I know how to take care of my health.

*Statistical Model:* OLS regression model with and without an interaction of Tech and Touch were reported.

*Covariates:* No covariates were added to this analysis.

*Sub-sample analysis:* No sub-sample analyses were considered for this outcome.

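### The tablet-provisioning offset is the wrong exposure for the outpatient session counts (H3 Outcomes 4 and 5), and the SAP disagrees with itself on which other models carry it and on what scale

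*SAP*

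**What the plan says.** SAP 1.4.2 gives one general rule: "we included the length of tablet provisioning, measured in days, as an offset parameter in all models". The only reason offered is that patients had the inpatient portal for different lengths of time. The section promises that departures from the general model will be noted later, but no H3 or H4 outcome section removes the offset.

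Footnote i to SAP 1.4.4 describes the model fitting. It says "This provision length was included as an exposure in the model fitting process" and concludes that "all count outcomes were fit using a negative binomial model with the provision length adjustment". That covers the two outpatient counts in H3 as well as the inpatient count in H1.

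H3 Outcomes 4 (SAP 1.7.4) and 5 (SAP 1.7.5) share one definition: "The count of MyChart sessions occurring between the date of enrollment in the study and the cutoff date". SAP 1.4.8 places the candidate cutoffs "before/after the hospital encounter in which an individual was enrolled in the study", and footnote ii reports that early adoption patterns "motivated us to set the value for the cutoff date at 90 days".

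The H4 self-efficacy scale (SAP 1.8.1) "was scored as the mean of six individual 5-point Likert scale survey items" and is analysed by OLS. That section lists no covariates and does not mention an offset.

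**The concern.** An offset enters a model with its coefficient fixed at 1. In a log-link count model, ln(time) as an offset turns counts into rates per unit of that time, so the time must be the period over which the events were counted. Tablet days meet that condition for inpatient sessions (H1 Outcome 1). They do not for outpatient sessions, most of whose counting window falls after the tablet has been handed back. As written, H3 Outcomes 4 and 5 report outpatient use per inpatient tablet day.

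The SAP also leaves open what was fitted elsewhere. SAP 1.4.2 covers every model and speaks of an offset in days. Footnote i covers count outcomes and speaks of an exposure, which by convention enters as ln(days). SAP 1.8.1 names neither. A reader cannot tell whether the OLS, logistic and fractional logistic models carried an offset, or on what scale. For OLS this matters, because a slope-1 offset means that the outcome analysed is the self-efficacy score minus the offset.

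At stake are the precision of secondary outcomes, their freedom from bias if tablet time differs by arm, and the ability to reproduce the analysis.

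**Working it through.** The documents give no figure for this choice, so there is nothing to reproduce. They also give no distribution of provisioning length, session counts or self-efficacy scores. Those inputs are assumed below.

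**1. Imposed ratio against counting window (H3 Outcomes 4 and 5).** From the SAP: the window opens at enrollment (1.7.4, 1.7.5) and closes 90 days after the enrollment stay (1.4.8, footnote ii). Assumed: patients with 15 and 3 tablet days, tablet held from enrollment to discharge.
- Ratio forced by an ln(days) offset: 15/3 = 5.
- Windows: 90 + 15 = 105 and 90 + 3 = 93 days; 105/93 = 1.129, about 13%.
- Slope on ln(days) that the window alone supports: ln(1.129)/ln(5) = 0.1214/1.609 = 0.075. The offset imposes 1.
- Protocol 5.1.1 has the tablet accepted before enrollment. A lag of 0 to 3 days for either patient gives window ratios from 102/93 = 1.10 to 105/90 = 1.17.
- An offset in untransformed days would force exp(12), more than 160,000-fold, so ln(days) is taken as the intended scale for counts.

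**2. Precision with provisioning balanced by arm.** Negative binomial simulation: N = 1,400, 31% High-Touch, rate ratio 1.2, mean 8 sessions, dispersion 1.5, robust standard errors, 200 runs (400 at slope 0.075). Tablet days are lognormal with median 5, cut at three days to mirror the length-of-stay exclusion in Protocol 6.3.8. This gives an SD of ln(days) of 0.34 to 0.58.

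| True slope on ln(days) | SE with offset / SE without |
|---|---|
| 0 | 1.08 to 1.18 |
| 0.075 | 1.07 to 1.16 |
| 0.25 | 1.04 to 1.09 |
| 0.5 | about 1.0 |
| 1 | 0.91 to 0.73 |

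The mean log rate ratio was 0.17 to 0.20 in all runs, against ln(1.2) = 0.182. With dispersion 3, the ratios at slope 0.075 are 1.05 and 1.13. A separate simulation (n = 1,000, mean 6, dispersion 1, SD of ln(days) 0.6, days allowed down to 1) gave empirical SEs of 0.095 with the offset and 0.071 without, a ratio of about 1.34. The size is therefore sensitive to the assumed spread.

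**3. Bias with provisioning unbalanced.** If tablet time is longer by a factor f in one arm and the true slope is b, the estimated ratio is multiplied by about f^(b − 1).
- f = 1.1, b = 0.075: 1.1^(−0.925) = 0.92. The n = 1,000 simulation gave 0.916 for a true ratio of 1.0.
- f = 1.2: 1.2^(−0.925) = 0.84. The simulation gave 0.842.
- With ln(90 + provisioning days) as the offset, the same simulations gave 1.006 and 1.000.

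**4. H4, if the rule is read literally.**
- Forced difference in score for 15 v 3 days: ln(5) = 1.61 points on the ln scale, or 15 − 3 = 12 points in raw days. The scale spans 4 points if scored 1 to 5 (assumed).
- With score SD s, SD of the offset v and true slope b, the SE ratio is √(s² + v²(1 − 2b))/s.
- ln(days), b = 0: s = 0.6, v = 0.34 gives √(0.36 + 0.116)/0.6 = 1.15; s = 0.6, v = 0.58 gives 1.39; s = 0.8 gives 1.09 and 1.24. At b = 0.5 the ratio is 1.00, and above that it is below 1.
- Raw days, b = 0: s = 0.7, v = 4 days gives √(0.49 + 16)/0.7 = 5.8.

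**5. Logistic and fractional logistic models.** With an ln(days) offset, simulated logistic treatment coefficients averaged 0.26 to 0.29, against 0.23 to 0.27 without. The fractional logistic Touch coefficient was 0.220 without and 0.222 with. The change is small.

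None of the simulations modelled clustering by hospital.

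**The case against.** **The adjustment was chosen on model fit.** Footnote i compares specifications by information criteria. It does not name the outcome compared, and its candidates include zero-truncated models. Those suit inpatient sessions, because Protocol 6.3.8 excludes participants with no Bedside use. They do not suit H3 Outcome 5, whose Prior MyChart Users are defined by sessions before enrollment and may have none afterwards. The comparison cannot justify the offset for that outcome.

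**The authors may never have put an offset in the OLS model.** This stands. Only the general sentence in SAP 1.4.2 points to one. Footnote i, which describes the fitting, speaks of counts alone. A reader might infer that the H4 analysis was wrongly run. The documents do not show that; they show sections that conflict.

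**The harm is undetermined.** Much of this stands. A reader might infer from the 0.075 slope that the offset must cost precision. That figure reflects window length only. The true slope also depends on how length of stay relates to later portal use, which no section reports, and near a slope of 1 the offset gains precision. A reader might also infer that the treatment effects are biased. With balanced provisioning they are not, and no imbalance is documented. It remains possible, because tablet time is partly determined after assignment: Protocol 3.1.3 lists tablets returned before the intervention.

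**The SAP is written in the past tense, so replacing its text could misdescribe what was run.** This stands and shapes the fix.

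**Conclusion.** The point holds for H3 Outcomes 4 and 5: inpatient tablet days are not the period over which outpatient sessions were counted. In the illustrative contrast the offset forces a 5-fold difference where the windows support about 1.13-fold, or 1.10 to 1.17 allowing for enrollment lag. With balanced provisioning the rate ratio is essentially unbiased. Its standard error could rise or fall: the main simulations run from 1.18 times to 0.73 times as the assumed slope goes from 0 to 1, and a wider assumed spread gives more. A 10% imbalance in tablet time would move a true ratio of 1.0 to about 0.92.

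For H4 the finding is an unresolved conflict between SAP 1.4.2, footnote i and 1.8.1. A fixed slope of 1 on self-efficacy has no stated basis, but its use is not established.

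The affected outcomes are secondary. A reader might extend the point to the primary hypotheses. That is not supported: tablet days are a fitting exposure for H1 Outcome 1, and the logistic and fractional logistic effects barely move under ln(days). The matter should be fixed, but it does not undermine the trial's main comparison.

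**What to change.** - In SAP 1.4.2, limit the provisioning offset to inpatient-use outcomes, with ln(provisioning days) as the exposure for H1 Outcome 1. Amend the clause on count outcomes in footnote i to match.
- For H3 Outcomes 4 and 5, use ln(days from enrollment to the cutoff date), or no offset.
- Use no offset in the H4 OLS model.
- State which models actually carried the offset, and whether it was days or ln(days). For the logistic and fractional logistic models this statement is all that is asked.
- Report provisioning days by arm.
- Where offset models were already run for H3 Outcomes 4 and 5 or H4, report them beside the respecified models and label the latter a correction, so that the record of what was done stays intact.

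The cost is one sentence, one footnote clause, a short disclosure, one descriptive table and a re-run of the affected models on existing data.
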